9.2. Duration of Observation

The duration of observation during the study (in days) will be calculated for each individual patient as:

(Date of last visit – date of first study drug administration) + 1 day

The duration of observation will be summarized descriptively by treatment group for the SAF population via the following summary statistics: arithmetic mean, sample SD, minimum, Q1, median, Q3, and maximum. In addition, the number and percentage of patients randomized and treated will be presented by the following, cumulative, duration of observation categories: ≥ 1 day, ≥ 15 days, ≥ 29 days, ≥ 43 days, etc., with a 14-day increment added for each subsequent category. The highest category displayed will account for the maximum duration of observation observed in the study.

9.3. Prior and Concomitant Medications

For each participant, medications will be recorded from the date of informed consent/assent through the end of the study (i.e., the EOS visit or, for participants who do not complete the EOS visit, the last available study visit). Medications will be coded using the World Health Organization-Drug Dictionary (WHO-DD).

Prior medications are defined as any medication with start date prior to the date of administration of the first dose of study drug. Per the CCG for this study, all medications given within the 12 months prior to the screening visit will be collected.

Concomitant medications are defined as any medication taken at any time on or after the date of administration of the first dose of study drug through the end of the study. Thus, concomitant medications include (i) medications with start date on or after the date of administration of the first dose of study drug and (ii) prior medications indicated as ongoing or with end date on or after the date of administration of the first dose of study drug. Concomitant medications will be further classified as follows:

- Concomitant medications taken during the 24-52-week treatment period are those medications taken at any time from the date of administration of the first dose of study drug up to the date of the EOT visit (or, if the EOT visit was not performed, the minimum of the date of administration of the last dose of study drug + 14 days and the date of patient last contact).
- Concomitant medications taken during the follow-up period are those medications taken at any time on or after the EOT visit (or, if the EOT visit was not performed, on or after the date of administration of the last dose of study drug + 15 days) through the date of patient last contact.

The number and percentage of patients taking prior/concomitant medications will be summarized, sorted by decreasing frequency of Anatomical Therapeutic Chemical (ATC) level 2 and ATC level 4 in the dupilumab treatment group. If a patient has multiple usages of a prior medication or multiple usages of a concomitant medication within the 24-52-week treatment period or within the follow-up period, the medication will be counted only once for the patient for the indicated reporting period. Patients will be counted only once for each medication class (ATC level 2 and 4) associated with a medication. Separate summaries will be provided for prior medications, concomitant medications taken during the 24-52-week treatment period, and for concomitant medications taken during the follow-up period. Summaries of prior medications and concomitant medications taken during the 24-52-week treatment period will be performed on the FAS population. Summaries of concomitant medications taken during the follow-up period will be performed on the subset of the FAS population who completed the treatment period and entered the follow-up period.

Prohibited Medications

Treatment with the following concomitant medications is prohibited during the study:

- Systemic immunosuppressive/immunomodulating drugs (including, but not limited to: omalizumab, cyclosporine, mycophenolate-mofetil, azathioprine, methotrexate, interferon gamma (IFN- γ), or other biologics) other than protocol-defined use of corticosteroids
- Treatment with an investigational drug (other than dupilumab)
- Initiation of subcutaneous immunotherapy (SCIT), or change in dose for those patients on a stable dose of SCIT within 1 year prior to screening
- Sublingual immunotherapy (SLIT)
- Oral immunotherapy
- Treatment with a live (attenuated) vaccine:
 - Chickenpox (varicella)
 - FluMist-influenza
 - Intranasal influenza
 - Measles (rubeola)
 - Measles-mumps-rubella combination
 - Measles-mumps-rubella-varicella combination
 - Mumps
 - Oral polio (Sabin)
 - Oral typhoid
 - Rubella
 - Smallpox (vaccinia)
 - Yellow fever
 - Bacille Calmette-Guerin
 - Rotavirus
 - Varicella zoster (shingles)

Blinded adjudication of prohibited concomitant medications will be performed by the Sponsor clinical team before database lock according to documented procedures.

The number and percentage of patients taking prohibited medications (as adjudicated by the Sponsor clinical team) at any time during the study will be summarized for the FAS population, sorted by decreasing frequency of ATC level 2 and ATC level 4 in the dupilumab treatment group. If a patient has multiple usages of a prohibited medication during the study, the

medication will be counted only once for the patient. Patients will be counted only once for each medication class (ATC level 2 and 4) associated with a medication.

Rescue Medications

Short-acting bronchodilators (SABAs) are permitted as rescue therapy throughout the study. Rescue therapy with ICS and/or LABAs is not permitted.

Systemic corticosteroids are allowed as rescue treatment for exacerbation. The need for rescue therapy and dosage will be determined by the site investigator. For patients on chronic systemic corticosteroids, an increase in the dose of systemic steroids is allowed as rescue treatment.

If 2 or more exacerbations occur during the treatment period, antifungal therapy may be initiated (or the dose may be increased for patients on antifungal therapy) after consultation with the medical monitor at the discretion of the investigator.

Patients receiving rescue therapy permitted by the protocol may continue to receive study drug. They will remain blinded and will be asked to return to the clinic for all remaining applicable study visits for the double-blind treatment period and the follow-up period, and participate in all assessments for these visits according to the Schedule of Time and Events specified in Section 14.2.

Blinded adjudication of rescue medications will be implemented before database lock by considering the type of medication, indication, timing, frequency, and the potential impact of the use of the medication. The rescue medications will be adjudicated by the Sponsor clinical team according to documented procedures.

The number and percentage of patients taking rescue medications (as adjudicated by the Sponsor clinical team) at any time during the study will be summarized for the FAS population, sorted by decreasing frequency of ATC level 2 and ATC level 4 in the dupilumab treatment group. If a patient has multiple usages of a rescue medication during the study, the medication will be counted only once for the patient. Patients will be counted only once for each medication class (ATC level 2 and 4) associated with a medication.

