5.2. Treatment Period Dispositions

The disposition of all randomized patients during the treatment period will be displayed by treatment group (as randomized). The number of treated patients (i.e., patients who received at least 1 dose of study drug) and the number of patients who complete the treatment period will be presented. A patient is considered to have completed the treatment period if they have an end of treatment (EOT) visit. As patients who discontinue study drug are allowed to remain in the study, the number of treatment period completers who remained on study drug throughout the entirety of the treatment period and those who permanently discontinued study drug early will be reported. Patients who permanently discontinued study drug early will be further summarized by reason for early study drug discontinuation (including COVID-19-related reasons).

The number of treatment period completers who proceed into the follow-up period will be reported. A patient will be considered to have entered the follow-up period if they had an EOT visit and the patient's date of last contact is after the date of the EOT visit. The disposition of patients who enter the follow-up period is described in Section 5.3.

Lastly, the number of patients who discontinue from the study during the treatment period (i.e., who have an early termination visit and no EOT visit in the database) will be presented. Patients who discontinue from the study early will be further summarized by reason for early discontinuation from the treatment period (including COVID-19-related reasons).

Corresponding percentages with respect to the number of randomized patients in each treatment group will also be presented for the aforementioned treatment period disposition statuses.

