7.2.2. Secondary and Exploratory Efficacy Analyses

The secondary efficacy endpoint of the annualized rate of severe respiratory exacerbations over the 24-52-week treatment period will be analyzed using a negative binomial regression model. The response variable will be the total number of events occurring during the treatment period. The negative binomial regression model will include OCS use at screening, OAF use at screening, region, number of severe respiratory exacerbations requiring treatment with systemic corticosteroids in the 12 months prior to the screening visit, baseline eosinophil count, and treatment group as covariates. The natural logarithm of the number of days from the date of the first dose of study treatment (or date of randomization for patients who are randomized but not treated) to the date of the EOT visit (or date of last contact for patients who are lost to follow-up or discontinue from the study prior to the EOT visit) divided by 365.25 will be used as the value of the offset variable for each patient. The estimated annualized event rate within each treatment group and the corresponding 2-sided 95% CI will be derived from the model. For patients who permanently discontinue from study treatment, any off-study treatment severe respiratory exacerbation events that occur through the patient's EOT visit (or date of last contact for patients who are lost to follow-up or discontinue from the study prior to the EOT visit) will be included in the analysis. [REDACTED]

The secondary efficacy endpoints of the annualized rate of ABPA-related exacerbations (i.e., those that are associated with a doubling of serum total IgE from the prior pre-exacerbation value) over the 24-52-week treatment period and the annualized rate of severe respiratory exacerbations requiring either hospitalization or observation for >24 hours in an ED/urgent care facility over the 24-52-week treatment period will be analyzed in a similar manner as the

annualized rate of severe respiratory exacerbations. [REDACTED]
[REDACTED]
[REDACTED]
[REDACTED]
[REDACTED]. For each of the aforementioned

endpoints analyzed via negative binomial regression, if the model fails to converge, only descriptive statistics will be provided for the annualized rate of events in each treatment group.

[figure not shown]

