Separate summaries will be provided for prior procedures, concomitant procedures performed during the 24-52-week treatment period, and for concomitant procedures performed during the follow-up period. If a patient has multiple records of a given prior procedure or multiple records of a given procedure within the 24-52-week treatment period or within the follow-up period, the procedure will be counted only once for the patient for the indicated reporting period. Summaries of prior procedures and concomitant procedures during the 24-52-week treatment period will be performed on the FAS population. Summaries of concomitant procedures during the follow-up period will be performed on the subset of the FAS population who completed the treatment period and entered the follow-up period.

Prohibited Procedures

The following concomitant procedures are prohibited during the study period:

- Major elective surgical procedures
- Bronchial thermoplasty

Blinded adjudication of prohibited concomitant procedures will be performed by the Sponsor clinical team before database lock according to documented procedures.

The number and percentage of patients with prohibited procedures (as adjudicated by the Sponsor clinical team) at any time during the study will be summarized for the FAS population, sorted by decreasing frequency of primary SOC and PT in the dupilumab treatment group. If a patient has multiple records of a given prohibited procedure during the study, the procedure will be counted only once for the patient.

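### In patients with no EOT visit, ordinary medications and procedures first started after last dose + 14 days fall into a follow-up class that no summary table can show

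*SAP*

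**What the plan says.** SAP 9.3 splits concomitant medications into two reporting periods.

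- **Treatment period.** It runs from first dose to EOT. Where that visit is missing, the rule is: "if the EOT visit was not performed, the minimum of the date of administration of the last dose of study drug + 14 days". Last contact applies instead if it comes earlier.
- **Follow-up.** It starts at the EOT visit or, where there was none, "on or after the date of administration of the last dose of study drug + 15 days", and ends at last contact.

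The treatment-period table uses the whole FAS. The follow-up table is "performed on the subset of the FAS population who completed the treatment period and entered the follow-up period".

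SAP 5.2 defines both conditions. On completion: "A patient is considered to have completed the treatment period if they have an end of treatment (EOT) visit". On entry: "A patient will be considered to have entered the follow-up period if they had an EOT visit" and the last contact falls after that visit.

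SAP 9.4 uses the same dates for procedures and the same restriction: "Summaries of concomitant procedures during the follow-up period will be performed on the subset of the FAS population who completed the treatment period". Entry into follow-up is again required.

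Two other provisions bear on the point. SAP 9.3 and 9.4 also tabulate rescue medications, prohibited medications and prohibited procedures, as adjudicated by the sponsor's clinical team, for the whole FAS at any time during the study. For exacerbation rates, SAP 7.2.2 closes the observation of a patient with no EOT visit at the "date of last contact for patients who are lost to follow-up or discontinue from the study prior to the EOT visit".

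**The concern.** The SAP writes a follow-up start date specifically for patients with no EOT visit, then defines a follow-up population that excludes every such patient. The branch cannot feed a table.

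The group is foreseen. SAP 2.1 and Protocol 8.4.2 encourage patients who stop study drug to stay in the study, and SAP 5.2 plans a count of those who leave during the treatment period with an early termination visit and no EOT visit. Someone who stops drug, stays more than 14 days and then leaves has in-study time that belongs to neither period table.

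At stake are the completeness of the medication and procedure tables and like-for-like reporting. Two patients who stopped drug on the same day and started the same new therapy on the same later day would be reported differently, depending only on whether an EOT visit took place. A new background controller is the clearest example: SAP 2.1 allows such changes after 2 or more exacerbations, and the rescue and prohibited text in SAP 9.3 does not name them as either.

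**Working it through.** The plan states no figure to reproduce, so the check follows records through the definitions.

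**Rules, for a patient with no EOT visit**

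1. End of treatment-period class = min(last dose + 14 days, last contact) (SAP 9.3, 9.4).
2. Follow-up class = last dose + 15 days through last contact (SAP 9.3, 9.4).
3. Membership of the follow-up table requires an EOT visit and a last contact after it (SAP 9.3 and 9.4, read with 5.2).
4. Rule 2's fallback applies only when there is no EOT visit. Rule 3 then always fails.

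**Illustrative patient** (invented; day = 7 × week + 1, matching the target days in SAP Table 3, such as Week 8 = Day 57)

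- Last dose Week 8 = Day 57; last contact Week 30 = Day 211; no EOT visit.
- Treatment-period class ends at min(57 + 14, 211) = Day 71 (Week 10).
- Follow-up class runs from 57 + 15 = Day 72 to Day 211, which is 211 − 72 + 1 = 140 days, or 20 weeks.

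| Record | Table reached |
|---|---|
| Ordinary medication or procedure, Days 100–110 | None |
| Same dates, adjudicated as rescue or prohibited medication, or prohibited procedure | Any-time FAS table |
| Medication started after first dose and by Day 71, continuing | Treatment period |
| Medication ongoing from before first dose | Prior and treatment period |
| Ordinary record, Days 100–110, same last dose but EOT visit on Day 169 | Treatment period |

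The first and last rows differ only in whether an EOT visit took place.

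**Sensitivity to the missed-dose rule.** Protocol 8.4.2.2, on temporary discontinuation, takes a patient out of the study after more than 4 consecutive missed doses. If that governed this patient, the fifth missed dose would fall at Week 18 (Weeks 10, 12, 14, 16, 18), which is Day 127. The window would then be 127 − 72 + 1 = 56 days, or 8 weeks. It shortens but does not close.

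**Number affected.** The documents give no count of patients who stop drug, remain more than 14 days and leave before EOT. Taking 1 to 4 of 60 purely as an assumption gives 1/60 = 2% to 4/60 = 7%. The number of records per patient cannot be derived.

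**The case against.** The strongest reply is that the information that matters most is kept elsewhere, and much of this stands.

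- **Not every record is lost.** A reader might infer that all therapy after last dose + 14 days disappears from the tables. It does not. Rescue and prohibited items have any-time FAS tables, and therapy begun by last dose + 14 days and continuing is already in the treatment-period table.
- **The primary estimand is not left uninterpretable.** A reader might infer that the therapy needed to interpret off-drug FEV1 under treatment policy is removed. The medication intercurrent events in SAP 7.2.1.1 are rescue systemic corticosteroids or oral antifungals, and prohibited medications. The any-time tables cover both. Biologics and immunosuppressants are on the prohibited list.
- **Weeks are not records.** In the example, 20 of 30 weeks (67%) lie outside both period tables. It is tempting to read this as two-thirds of the medication records. The SAP counts a medication once per patient per period, so continued use adds nothing and no share of records follows.
- **Different windows are not an error in themselves.** SAP 7.2.2 sets time at risk for an event rate; SAP 9.3 sets a reporting window, and its 14-day cut matches the on-treatment safety period in SAP 10.
- **The group is probably small.** Patients who stop drug but stay to an EOT visit have everything up to that visit in the treatment-period table.

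The reply does not rescue the no-EOT follow-up branch, which still leads nowhere. The any-time tables hold only adjudicated items, and for procedures only prohibited ones. Listings are no sure backstop, because SAP 1.4 limits them to those required for the study report.

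**Conclusion.** The defect is real and narrow. Followed as written, SAP 9.3 and 9.4 leave out of every summary the non-rescue, non-prohibited medications and the non-prohibited procedures that first start between last dose + 15 days and last contact in patients with no EOT visit. This follows from the SAP's own definitions and needs no outside assumption.

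The effect is confined to descriptive tables. No primary or secondary efficacy estimate changes, and the medication intercurrent events of the primary estimand remain tabulated. The window is 20 weeks in the illustrative patient, or 8 weeks if the missed-dose rule ended participation at the fifth missed dose. How many patients or records are involved is unknown. This is a minor correction, worth making because the SAP evidently meant these patients to be reported somewhere.

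**What to change.** Either of two changes to SAP 9.3 and 9.4 closes the gap.

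1. **Preferred.** For patients with no EOT visit, end the treatment-period class at the date of last contact, and delete the follow-up branch that starts at last dose + 15 days. Medications, procedures and exacerbations would then share one end date for these patients, consistent with SAP 7.2.2.
2. **Alternative.** Keep the period definitions and let the follow-up tables include every FAS patient with time in the follow-up class, whether or not there was an EOT visit. The denominators of those tables would then no longer match the follow-up disposition in SAP 5.3, so a footnote would be needed.

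The cost is an edit to the period definitions or table populations in two sections and a programming change; no new data are needed. The drawback of the first option is that the treatment-period table takes in off-drug time for these patients. It already does so for off-drug patients who have an EOT visit.

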9.4. Prior and Concomitant Procedures

For each participant, procedures will be recorded from the date of informed consent/assent through the end of the study (i.e., the EOS visit or, for participants who do not complete the EOS visit, the last available study visit). Procedures will be coded using the MedDRA® dictionary.

Prior procedures are defined as any procedure performed prior to the date of administration of the first dose of study drug.

Concomitant procedures are defined as any procedure performed at any time on or after the date of administration of the first dose of study drug through the end of the study. Thus, concomitant procedures include (i) procedures with start date on or after the date of administration of the first dose of study drug and (ii) prior procedures indicated as ongoing or with end date on or after the

date of administration of the first dose of study drug. Concomitant procedures will be further classified as follows:

- Concomitant procedures performed during the 24-52-week treatment period are those procedures conducted at any time from the date of administration of the first dose of study drug up to the date of the EOT visit (or, if the EOT visit was not performed, the minimum of the date of administration of the last dose of study drug + 14 days and the date of patient last contact).
- Concomitant procedures conducted during the follow-up period are those procedures conducted at any time on or after the EOT visit (or, if the EOT visit was not performed, on or after the date of administration of the last dose of study drug + 15 days) through the date of patient last contact.

The number and percentage of patients with prior/concomitant procedures will be summarized, sorted by decreasing frequency of primary SOC and PT in the dupilumab treatment group.

Separate summaries will be provided for prior procedures, concomitant procedures performed during the 24-52-week treatment period, and for concomitant procedures performed during the follow-up period. If a patient has multiple records of a given prior procedure or multiple records of a given procedure within the 24-52-week treatment period or within the follow-up period, the procedure will be counted only once for the patient for the indicated reporting period. Summaries of prior procedures and concomitant procedures during the 24-52-week treatment period will be performed on the FAS population. Summaries of concomitant procedures during the follow-up period will be performed on the subset of the FAS population who completed the treatment period and entered the follow-up period.

Prohibited Procedures

The following concomitant procedures are prohibited during the study period:

- Major elective surgical procedures
- Bronchial thermoplasty

Blinded adjudication of prohibited concomitant procedures will be performed by the Sponsor clinical team before database lock according to documented procedures.

The number and percentage of patients with prohibited procedures (as adjudicated by the Sponsor clinical team) at any time during the study will be summarized for the FAS population, sorted by decreasing frequency of primary SOC and PT in the dupilumab treatment group. If a patient has multiple records of a given prohibited procedure during the study, the procedure will be counted only once for the patient.

